Indeed, taVNS have been shown to be a safe, portable, and feasible tool (50, 51). Our group has demonstrated its safety through a systematic review and meta-analysis on the topic (Safety of transcutaneous auricular vagus nerve stimulation(taVNS): A systematic review and meta-analysis – peer review). Moreover, several studies have shown promising results of taVNS to treat various disorders such as depression, anxiety, Alzheimer's disease, headache, obesity, and diabetes(2, 52-55). However, no mechanistic studies have investigated the taVNS neural network and autonomic nervous system's effects of this technique. Therefore, we aim to assess how taVNS can affect EEG metrics and HRV and assess its safety. Also, we aim to evaluate predictors that can influence the response to taVNS, so understanding the variables associated with response to taVNS can help the design of future clinical trials to maximize the effects of this intervention.

2. Specific Aims and Objectives

Our goal is to perform an exploratory, mechanistic randomized double-blind sham-control trial in healthy participants, to assess the physiologic effects of a single session of bilateral taVNS, on neural networks and autonomic function.

The specific aims of this experiment are as follows:

Aim 1: We aim to compare the neurophysiologic effects of a single session of active taVNS versus sham taVNS in Frontal Alpha Asymmetry, Functional Connectivity and Phase Synchrony of DMN using EEG on a processing emotional facial expressions and a Go/NoGo task. We expect to find differences in face-related frontal alpha asymmetry between active taVNS versus sham taVNS in healthy controls. Also, regarding the DMN, we expect that taVNS decreases FC between DMN and other areas.

Aim 2: As a second aim, we will measure the effects of one active taVNS session versus sham in heart rate variability total power, very low frequencies (VLF), low frequencies (LF), and high frequencies (HF), and LF/HF ratio. We expect the taVNS to increase HF and decrease LF/HF ratio due to parasympathetic activation. Furthermore, the standard deviation of the R-R intervals (SDRR), the count of R-R intervals that differed more than 50 ms (NN50), the percentage of NN50 (pNN50), and the root mean square of the difference between successive R-R intervals (RMSSD) will be measured and we expect an increase on those metrics as well. We will also explore a non-linear method to calculate the short-term detrended fluctuation exponent (DFA-alpha1).

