6. STUDY PROCEDURES

Study Outline

Pre-screening Procedures:

During the pre-screening process, the subject can contact a co-investigator, usually via encrypted Zoom Enterprise call, and REDCap form. During the pre-screening process, the co-investigator will discuss the details of the study, explain the study procedures, and encourage the subject to ask questions. In the privacy of the encrypted Zoom Enterprise call for healthcare, the co-investigator will ask the subject questions from the following:

- 1) Online Screening questionnaire
- 2) Phone Pre-screening questionnaire

Once this information is collected, the co-investigator will consult with the PI regarding the eligibility of the subject, who will then give the approval for the subject to come to our laboratory for the screening procedure.

Visit 1

Online or in-person Screening and Consent Visit – (Approximate Time: 1 hour)

If in-person, the visit 1 can be performed together with the visit 2 - (Approximate Time: 3 hours and 30 min).

If done remotely; the documentation would be signed electronically, and the visit would be done by telephone or using Zoom Healthcare)

During the Screening, the PI and/or a co-investigator will conduct once more a review of inclusion/exclusion criteria to determine the subject's eligibility for enrollment. If the consent is conducted by the co-investigator, the PI will review and sign off. Study procedures will be reviewed with the subject, and documentation of informed consent will be obtained. We will use an encrypted web-based platform (REDCap e-consent module) via Zoom call (Enterprise plan). Both services are already validated and in use by the MGB network.

- Discuss study-specific procedures with the subject.
- Review inclusion and exclusion criteria.
- Obtain a signed and dated consent form.
- Conduct a Demographics Survey, Brief Medical History, Beck depression inventory (BDI), and the Edinburg Handness Inventory Short form (EHI/SF).

Visit 2

Baseline Visit and First taVNS session – (Approximate Time: 2 hours and 30 min).

Urine pregnancy exam (if applicable).

Baseline assessments:

- EEG
- HRV
- QST
- The Brief Mood Introspection Scale (BMIS)
- Visual Analogue Scale to Evaluate Fatigue Severity (VAS-F) adaptation using tiredness item.

After the Baseline assessments:

Subjects will receive one session of either active taVNS or sham taVNS for 60 min. During the stimulation both groups will also be assessed with EEG, HRV, and VAS-F.

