After the session, subjects will complete the following assessments:

- Side Effects Questionnaire for taVNS.
- Questionnaire to assess the success of blinding in clinical trials.
- EEG
- HRV
- QST
- BMIS
- VAS-F

Upon arrival and prior to the application, taVNS intensity will be measured for each participant separately, as above the detection threshold and below the pain threshold. The stimulation electrodes will be applied bilaterally to the ears, and in order to individually adjust the stimulation intensity, participants will receive increasing and decreasing series of 10-s stimulation trials and will rate the subjective sensation of the stimulation in a 10-point scale, ranging from nothing (0), light tingling (3), strong tingling (6), to painful (10). The increasing series of trials will start from an intensity of 0 mA and increase by 0.3 mA on a trial-by-trial basis until participants report it is uncomfortable to continue. This procedure will be repeated a second time. The final stimulation intensity for the experimental procedure will be calculated based on the average of the two intensities just below pain threshold.

We will use a Healaon Transcutaneous Auricular Vagus Nerve Stimulation (taVNS) device (Neurive Inc., Gimhae, South Korea), which consists of an earset, with conductive eartips placed on the auricular concha of the ears. Electrodes are connected to a stimulator, and during active stimulation, both the cyma conchae of the auricular are stimulated at 30Hz, 200-250 us, with adjustable intensity for 60 min. The sham intervention will be done at the same location bilaterally to the cyma conchae of the auricular, however the device will be off during the 60 min session.

Data for this study will be collected from subjects using an electronic format capture system (REDCap), and each subject will be assigned a de-identified code to collect the data. The data entered will be securely transferred to the Mass General Brigham REDCap database, to which only IRB-trained and approved study staff will have access. The following assessments will be performed:

Demographic data: This survey will ask about demographic characteristics, including age, gender, sex, race, ethnicity, educational level, hand dominance, weight, height, and body mass index.

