Side Effects Questionnaire for taVNS: After the stimulation session, subjects will complete a questionnaire to evaluate potential adverse effects of taVNS on a 4-point scale (None, mild, moderate, and severe). They will be asked whether they have experienced any side effects in an open-ended manner and they will then be specifically asked about ear pain, headache, tingling, dizziness, skin redness, fatigue, prickling, pressure, itching, unpleasant feelings. If any side effects are reported, the degree of relatedness to the intervention will be assessed on a 5-point scale. This type of adverse events questionnaire has been suggested in our recent systematic review and meta-analysis on safety of taVNS and has been used similarly in all the tDCS studies of the group.

Questionnaire to assess the success of blinding in clinical trials: After the stimulation session, subjects will be asked to guess their treatment assignment, and they may be allowed to express treatment guess or uncertainty, i.e. subjects will be asked to guess their treatment assignment among active, sham or do not know. After that they will be asked how confident they are from 0 to 5 on their choice.

7. Risks and Discomforts

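### Intensity titration gives real current to every participant, sham included; its order relative to the baseline recordings is not fixed, and the single side-effects form cannot separate it from the session

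*Combined protocol and SAP*

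**What the plan says.** Two parts of Section 6 bear on this, together with the visit table in Section 3.

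- **Visit 2 outline.** It lists baseline EEG, HRV, QST, BMIS and VAS-F. After these, "Subjects will receive one session of either active taVNS or sham taVNS for 60 min". Titration is not a step in this sequence, and the visit table has no row for it.
- **Intensity-setting paragraph.** It comes after the list of post-session assessments and begins: "Upon arrival and prior to the application, taVNS intensity will be measured for each participant separately". On method: "The stimulation electrodes will be applied bilaterally to the ears", and "participants will receive increasing and decreasing series of 10-s stimulation trials and will rate the subjective sensation of the stimulation". The increasing series starts at zero, with an instruction to "increase by 0.3 mA on a trial-by-trial basis until participants report it is uncomfortable to continue". Then: "This procedure will be repeated a second time".
- **Sham.** The earset goes in the same place, with the stimulator switched off for the hour. This describes the session only; no exemption from titration is stated.
- **Side effects.** "After the stimulation session, subjects will complete a questionnaire to evaluate potential adverse effects of taVNS on a 4-point scale". The visit table shows this form once, in the post-intervention column. The prompted items include ear pain, tingling, prickling and unpleasant feelings. No recall period is given.
- **Purpose.** Section 1 closes by saying that "we aim to assess how taVNS can affect EEG metrics and HRV and assess its safety". Section 9 plans differences from baseline for the HRV metrics (Aim 2) and EEG measurement at baseline and during stimulation (Aim 1).

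**The concern.** Two separate things are at stake.

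The first is what baseline means. If titration happens on arrival, all five baseline assessments are made after both ears have been stimulated up to discomfort, with no washout stated. The trial is mechanistic and enrols only people who have never had taVNS, so an unstimulated baseline is part of its purpose. The within-arm changes in Aim 2 would then describe movement from a state of unknown recent stimulation.

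The second is what the sham side-effect rate means. Sham participants will have felt real stimulation, and the only side-effects form comes after everything is over. A sham participant who reports tingling or ear pain from titration is answering truthfully. The sham rate becomes the rate for titration plus device off, which is not the rate for an unstimulated control.

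**Working it through.** The plan states no total for titration exposure, so there is no figure of its own to reproduce.

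**1. Order.** The intensity paragraph gives two time markers: arrival, and before the application. The first, read literally, puts titration ahead of baseline. The second also fits titration between baseline and session. The paragraph's position, after the post-session list, does not help, and neither the outline nor the visit table settles it. The order is therefore not fixed, and the literal reading is the unfavourable one.

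**2. Exposure.** Inputs from Section 6: steps of 0.3 mA, 10 s per trial, two runs. Assumption: discomfort at T mA, which the documents do not give. The length of the decreasing series is also not given, so both cases are shown.

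Seconds of current = (T / 0.3) × 10 × 2, doubled if a decreasing series of equal length is run.

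| Assumed T (mA) | Increasing only (s) | With equal decreasing series (s) |
|---|---|---|
| 0.9 | 60 | 120 |
| 1.5 | 100 | 200 |
| 3 | 200 | 400 |
| 6 | 400 | 800 |

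At T = 3 this is 200/3600 = 5.6% to 400/3600 = 11.1% of the 60-minute active session. For comparison, one HRV recording lasts 5 minutes (300 s). Two minutes is reached at 1.8 mA with the increasing series only, or at 0.9 mA with both.

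**3. Effect on changes from baseline.** Let d be the session effect at the reading during stimulation, b the titration after-effect present at baseline, and r the part still present during the session. Randomisation and identical titration make b and r the same in both arms on average. If effects add:

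- active change = (d + r) − b
- sham change = r − b
- active minus sham = d

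With titration first and its effect gone by the later reading (r = 0), the active change is d − b and the sham change is −b. Both within-arm changes are shifted, and the contrast is not. With titration after baseline (b = 0), the changes are d + r and r, and the contrast is again d. The documents give no value for b or r.

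**4. Effect on side effects.** The titration rating scale is anchored on light tingling, strong tingling and pain, so it provokes the sensations that the form later asks about. Let q be the share of participants who have a titration sensation and report it on the form, and let s_A and s_S be the probabilities of a session event in the active and sham arms, independent of titration sensations.

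- active rate = q + (1 − q)s_A
- sham rate = q + (1 − q)s_S
- difference = (1 − q)(s_A − s_S)

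The sham rate cannot be below q. As illustration, assumed values of q of 10%, 25% and 50% leave 90%, 75% and 50% of the true difference. This does not depend on whether titration comes before or after baseline.

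**The case against.** The strongest reply is that the plan nowhere says baseline follows titration. The words about the application are compatible with titration between baseline and session, and a trained team would probably work that way. This stands: a contaminated baseline is a consequence of the literal reading, not an established fact.

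A reader might also infer that leftover titration effects in sham weaken the active-sham contrast and cost power. The documents do not support this. Both arms are titrated alike, so an additive residual leaves the contrast at d. Dilution would need titration to add less in the active arm than in sham, for instance through a ceiling, and nothing in the plan says so. Nor do the documents state that participants receive minutes of current: that depends on a discomfort level and a series length they do not give.

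On side effects, it can be said that safety is not among the aims in Section 2, that the readable part of Section 9 plans no active-sham test of side effects, and that the form grades severity and relatedness. The first two limit the weight of the point. Text between Sections 9 and 12 is unreadable, so nothing can be concluded from it about adverse-event handling. Severity grades carry information that the yes/no formula ignores, and independence is an assumption. The relatedness rating does not solve the problem: a titration sensation in a sham participant really is related to taVNS, and the rating does not record when it occurred.

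**Conclusion.** The point holds in two parts.

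- **Baseline, conditional on order.** The outline and the intensity paragraph must be reconciled. If titration comes first, the baseline values are not pre-stimulation values and the within-arm changes in Aim 2 cannot be read as changes from an unstimulated state. The size cannot be estimated from the documents. The randomised active-sham contrast is not shown to be biased, and no power loss can be derived.
- **Side effects, under either order.** The sham rate is that of titration plus device off. A comparison of the arms on whether an event was reported is pulled towards zero, by (1 − q) under independence. This assumes that participants report titration sensations when asked after the session; with no recall window, nothing tells them not to. The value of q is unknown.

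This should be corrected before enrolment, because titration and session sensations cannot be told apart afterwards. It does not undermine the primary EEG comparison.

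**What to change.** 1. Reconcile the Visit 2 outline, the intensity paragraph and the visit table so that all baseline assessments are completed before any current is delivered, and show titration as its own step.
2. Give the existing side-effects questionnaire once more, after titration and before the session, to all participants.
3. In the active-sham comparison, count only events that start or worsen after session start. Report titration events separately for all participants.
4. Fix the timing of the EEG and HRV recordings during stimulation, identical in both arms and preferably later in the session.

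The cost is protocol wording and about 2 minutes for the extra questionnaire. The downside is that titration moves closer to the session. On the literal reading, about 60 minutes of baseline work separate the two, and that gap is lost. Item 4 is there for this reason: a later, common recording time gives any after-effect time to fade.

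### The side-effects checklist has no pre-session score, so symptoms already present before stimulation can be reported as side effects and dilute the comparison with sham (minor)

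*Combined protocol and SAP*

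**What the plan says.** The Side Effects Questionnaire paragraph in section 6 sets the timing: "After the stimulation session, subjects will complete a questionnaire to evaluate potential adverse effects of taVNS on a 4-point scale". The visit table in section 3 agrees, with one mark under Post intervention and none under Baseline or Intervention. An open question comes first ("They will be asked whether they have experienced any side effects in an open-ended manner"), followed by prompts for "ear pain, headache, tingling, dizziness, skin redness, fatigue, prickling, pressure, itching, unpleasant feelings". Attribution is handled by one further step: "If any side effects are reported, the degree of relatedness to the intervention will be assessed on a 5-point scale". The paragraph does not say who rates relatedness, what score counts as related, or whether only new or worsened symptoms are to be reported.

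Under Visit 2, baseline EEG, HRV and pain testing come before the session. Section 6 also has stimulation intensity set for each participant beforehand, by rising series of short stimulation trials at both ears taken to discomfort and then repeated. EEG and HRV are recorded again during the session. The list introduced by "After the session, subjects will complete the following assessments" puts the side-effects form first, ahead of the post-session EEG, HRV and pain tests, but does not say that the order is binding.

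Two related measures do have a baseline: mood (BMIS) and tiredness ("Visual Analogue Scale to Evaluate Fatigue Severity (VAS-F) adaptation using tiredness item"). On purpose, section 1 says "we aim to assess how taVNS can affect EEG metrics and HRV and assess its safety". Section 9, as far as it can be read, describes no analysis of side effects.

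**The concern.** Headache, fatigue, dizziness, pressure, itching and unpleasant feelings are common complaints that need not come from the device. A healthy volunteer may arrive with one, or acquire one from the electrode array, the heat and cold pain tests or the titration. Titration adds ear sensations as well and, as written, applies to both arms. With no earlier score on the same form, a symptom that preceded the session looks the same as one that the session caused.

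What is at stake is the safety description. Background symptoms raise the reported rate in both arms and shrink the gap between them, so a real difference in tolerability becomes harder to see and is more easily summarised as no difference from sham. A missing baseline cannot be reconstructed afterwards.

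**Working it through.** **The plan's own figure.** Section 9 gives d = 0.94, alpha 5% and power 80%. Two-sided, n per arm = 2(1.96 + 0.84)² / 0.94² = 17.7, rounded up to 18, or 36 in total. Then 36 × 1.20 = 43.2, rounded up to an even 44, or 22 per arm. The figure reproduces. It is driven by EEG alpha asymmetry; no sample-size statement concerns side effects.

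**Dilution model.** Let q be the true session-caused probability of any symptom in an arm, and b a background probability that is equal in both arms by randomisation and independent of q.

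- Observed rate: p = 1 − (1 − q)(1 − b) = b + (1 − b)q.
- Observed difference: p(active) − p(sham) = (1 − b)[q(active) − q(sham)].

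The sign of the difference is preserved and its size shrinks by the factor (1 − b).

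**Inputs.** 22 per arm comes from section 9. All values of q and b are assumptions, because the documents give none. Power is an exact enumeration of the two-sided Fisher test at 5%.

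| True q, active v sham | b | Observed rates | Difference (points) | Power |
|---|---|---|---|---|
| 50% v 10% | 0 | 50% v 10% | 40 | 79% |
| | 10% | 55% v 19% | 36 | 60% |
| | 20% | 60% v 28% | 32 | 45% |
| | 30% | 65% v 37% | 28 | 34% |
| 40% v 5% | 0 | 40% v 5% | 35 | 77% |
| | 10% | 46% v 14.5% | 31.5 | 52% |
| | 20% | 52% v 24% | 28 | 36% |
| | 30% | 58% v 33.5% | 24.5 | 26% |
| 30% v 5% | 0 | 30% v 5% | 25 | 51% |
| | 20% | 44% v 24% | 20 | 19% |
| 20% v 5% | 0 | 20% v 5% | 15 | 20% |
| | 10% | 28% v 14.5% | 13.5 | 12% |

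Worked line: at 50% v 10% and b = 20%, active is 0.20 + 0.80 × 0.50 = 0.60 and sham is 0.20 + 0.80 × 0.10 = 0.28. The difference is 0.32 = 0.80 × 0.40.

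**What a baseline form recovers.** It removes only symptoms present before the session. Those arising during the 60 minutes from the array or from sitting still are new in both arms. Suppose a 20% background splits into equal pre-session and in-session parts. Each part is 1 − √0.80 = 10.6%. With the pre-session part removed, b = 10.6% remains and power at 50% v 10% is 59%. That is better than 45%, but not 79%.

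**The case against.** The case for leaving the plan alone has real content.

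- *Attribution is not ignored.* A reader might infer that every background symptom will be counted as a taVNS side effect. The documents contain no such rule: a relatedness rating follows any report. This stands. The narrower point is that the rating is made without a prior score and has no stated rater, cut-off or use. Nor can one assume an unblinded rater, since section 5 says outcome assessors are blinded. Pages between section 9 and the references are unreadable, so absence of a side-effect analysis is established only for the readable text.
- *The sham arm protects the contrast.* Both arms have the same assessments, so a reader who infers a spurious or reversed difference goes too far. This stands; what remains is attenuation.
- *Timing.* A reader might take the form to come at the very end of the visit, after the second round of pain tests. The list in section 6 places it first after the session. Section 7 expects no EEG discomfort and only brief discomfort from the pain tests, so carry-over is possible but not shown.
- *Some items are partly covered.* Tiredness and mood have baselines. Skin redness and ear pain probably have little background on arrival, although titration could cause ear symptoms.
- *Rates may be low.* Section 7 reports low adverse-event incidence in the group's own review and no difference from controls. At 20% v 5%, power is about 20% even with no background, so a test would say little either way.

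None of this supplies a pre-session score, and the remedy is very cheap.

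**Conclusion.** The point holds as a minor design weakness. The checklist is taken once, after the session, so symptoms that precede stimulation can be reported as side effects, and the only filter is an underspecified relatedness rating. The consequence is inflated rates in both arms and a risk difference scaled by (1 − b), with its direction intact.

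The size in this trial cannot be computed. The illustrative fall from 79% to 34% power rests on assumed rates of 50% v 10%, independent background of up to 30%, 22 analysed per arm and a Fisher test that the readable plan does not specify. It should not be read as the loss that a baseline form would repair, because symptoms arising within the session stay in the count. Safety is named as an aim in section 1 but is in neither Aim 1 nor Aim 2, is not a primary outcome and is not powered. N = 44 is unaffected.

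**What to change.** 1. Give the same checklist once, immediately before the 60-minute session and after EEG set-up, the baseline pain tests and titration. Add it to the Baseline column of the visit table.
2. Make the main side-effect summary, by arm, the items that are new or at least one grade worse than the pre-session score.
3. Keep raw post-session rates and relatedness as secondary descriptions, and state who rates relatedness and how the scale is summarised.
4. State that the post-session form is completed before the post-session EEG and pain tests, as the list order already suggests.

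The cost is about 2 minutes per participant, one table entry and one analysis definition, with no change to the sample size. There are two downsides. Asking early may prime participants to notice symptoms, equally in both arms. Ear symptoms that persist from titration would also be treated as baseline, which is why the raw rates should be shown alongside.
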